counseling by a pediatric exercise physiologist + interactive accelerometer, or office provider counseling (standard of care). The intervention group will be asked to continue to wear the accelerometer everyday (most waking hours) and log their activity by regularly (3 times a week) uploading the device for a period of 3 months, use of the internet must be supervised by a parent or guardian. Their activity will be monitored via the online site on a regular basis by study personnel and feedback will be provided at least once a week through email and/or phone calls. At the end of the intervention all participants will be asked to again wear the accelerometer for 1 week to assess physical activity, and complete questionnaires assessing attitudes towards and self-efficacy around physical activity. Lipid levels and blood pressures, when obtained for clinical visits in Preventive Cardiology Clinic, will be evaluated for change over the course of the intervention. Participants will be given a non-invasive pulse wave velocity test. Pulse wave velocity testing is a painless non-invasive test to evaluate the time it takes for blood to move from the heart to the rest of the body. In practice, this involves using a fingertip probe placed lightly on the brachial artery – the internal aspect of the elbow, the carotid artery – side of the neck, and the femoral artery – groin area. This final measurement is easily performed through light clothing. In order to coordinate the timing of the pulse wave, four EKG electrodes are placed on the patient. The entire procedure takes about 15 minutes in experienced hands. There is no risk involved in this non-invasive procedure. It is less painful than a blood pressure measurement. The research study will require 2 visits to the Preventive Cardiology Clinic in Boston or Waltham, based on their preference. Each visit may take up to 1-1.5 hours.

b. Patient Selection and Inclusion/Exclusion Criteria

A sample of 60 patients at increased risk for atherosclerosis will be recruited from Preventive Cardiology.

Inclusion criteria:

Subjects will be eligible for enrollment based on the following criteria:

- 1) Patients at increased risk of atherosclerosis based on lipid profiles (TC > 199 mg/dL, HDL < 40 mg/dL, LDL > 129 mg/dL, blood pressure (SBP or DBP > 90th percentile), obesity (>85%BMI)
- 2) Ages 13-21 years
- 3) Reporting an average of less than 60 minutes per day of moderate to vigorous exercise most (5) days of the week.

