- iii. WHO will be responsible for subject recruitment?

Providers from the Preventative Cardiology Program including MDs, RNs and PNPs and Exercise Physiologists, Lead EKG Technician, Research Fellow, and Research Assistant from Children's Hospital Cardiovascular Clinic will recruit subjects by phone, mail, and clinic visit.

Main Study Consent (during Clinic Visit): Participants will be asked to provide informed consent/assent during their clinic visit.

d. Description of Study Treatments or Exposures/Predictors

Treatment for the study involves randomizing participants into FITT exercise counseling in conjunction with an interactive accelerometry tool (intervention) and physician counseling alone (standard of care/control) The FITT principle is based on standard exercise prescription guidelines supported by the American College of Sports Medicine (ACSM). FITT stands for Frequency – the number of days per week one exercises, Intensity – how hard one exercises, Type – aerobic vs. non aerobic exercises, Time – the duration of the exercise session. The ACSM combined with the Center for Disease Control and Prevention (CDC) recommendations for aerobic activities for children and adolescents should do 60 minutes or more of physical activity daily. Activities should consist of aerobic type exercises, most of the 60 minutes or more per day should be moderate or vigorous intensity. Vigorous intensity should be at least 3 days per week. Muscle strengthening physical activities and bone strengthening activities should be incorporated at least 3 days per week as part of the 60 or more minutes. Patients will be counseled on this principle and each participant will receive a personal exercise prescription based on the FITT principle, as well as monthly phone follow-up.

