Participates who engage in FITT exercise counseling in conjunction with accelerometry will also receive a BodyMedia arm band with an online subscription. BodyMedia FIT is a weight management system consisting of the BodyMedia Armband monitor and an online Activity Manager. The BodyMedia FIT Armband estimates the calories burned during your daily activities based on heart rate, perspiration, movement in space — from working out to doing homework; additionally, BodyMedia monitors the quality of sleep, an important factor in weight loss. The information tracked can easily be managed with BodyMedia's online Activity Manager. Patients have the ability to add in a food log, a feature that could improve weight loss by virtue of the logging function. Patients will just plug the unit into their computer's USB port each day to automatically upload info; the device stores up to 14 days of data, a feature that allows a little bit of flexibility for a busy team. Participants can simply log the food they ate via the computer. The activity Manager tool gives the patient and research team a running report of progress toward their goals, including steps taken, time spent in moderate and vigorous activity, nutritional

analysis and sleep efficiency, including any personal bests. The research team will review patient's data on a weekly basis and discuss the findings via phone or email to promote patient compliance and answer any questions or concerns they may have.

Participants that do not receive intervention will be provided a personalized FITT exercise counseling session following the study.

e. Definition of Primary and Secondary Outcomes/Endpoints

Measurements:

Accelerometry and Energy Expenditure: BodyMedia Armband technology incorporates accelerometry, temperature, moisture evaporation (reflecting sweat) and heart rate into algorithms designed to assess energy expenditure.

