Patients enrolled in the study will be informed that the research data collection will add about an hour to their current clinical visit. However, patients will gain information about their exercise capacity.

Table 1 Data Collection Schedule

Measures	Baseline visit	12-week visit	Minutes
Height, weight, blood pressure	X	X	10
Arterial Stiffness	X	X	20
Fasting lipids, glucose, insulin, HgnA1C, CRP, ALT	X	X	20
Accelerometry	X	X	10
Questionnaires	X	X	20
Chart Review for Medical History	X	X	20
Study Total			100

g. Study Timeline (as applicable)

See Table 2. Study recruitment will start in April of 2011 and continue until target enrollment is reached or funding is exhausted.

Table 2 Study Timeline (2011)

Study Event	Mar	Apr	May	Jun	Jul	Aug	Sep	Oct	Nov	Dec	Jan	Feb	Mar
Recruitment		X	X	X	X	X	X	X	X	X			
Consent/ Baseline		X	X	X	X	X	X	X	X	X			
Patient Follow-up		X	X	X	X	X	X	X	X	X			
12-Week Assessment					X	X	X	X	X	X	X	X	X

h. Adverse Event Criteria and Reporting Procedures

Adverse events are not anticipated as part of this intervention based on the nature of the activity involved. Serious events requiring medical attention will be reported immediately to Drs. [name] and [name] as well as to CCI per the reporting policy.

- i. If the Investigator is the Sponsor/Assignee (IND or IDE-holder), he/she is responsible for selecting a qualified monitor who will monitor the progress of all clinical investigations conducted under the IND or IDE. Please describe the monitoring plan for this protocol below:**

↳ Note: the EQuIP office provides monitoring services and advice. For info, contact EQuIP @ [name].

Not applicable

5. Data Management and Statistical Analysis

Data Management Methods

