The physical activity recommendations given as part of this protocol are based on national guidelines, modified for the individual based on exercise testing data. Physical activity is generally recommended for obese children and adolescents. The study does not employ pharmacological agents or notably invasive procedures. Thus, this study poses minimal risk to subjects. For this reason, the data and safety monitoring plan (DSMP) will focus on 1), 2) injury issues related to initiating new physical activities, 3) web-based communications, and 4) enrollment and drop-out rates. Subjects will be closely monitored by the study team. Serious adverse events will be promptly reported to the funding group and the Institutional Review Boards (IRB) of Children's Hospital Boston.

The frequency of data review is summarized in Table 3. The study director will be responsible for assembling the data and producing summary reports for review by the Research Team and the DSMB.

Table 3

Data type	Frequency of review
Subject accrual	Monthly
Drop-out rate	Monthly
Data collection and completion	Quarterly
Adverse events (injuries)	Quarterly
BodyMedia Online Activity Manager	Weekly

- Clinical Data: If significant medical conditions are discovered as part of the research protocol, participants and primary care physicians will be notified by phone and by mail, as appropriate, and referral for evaluation or treatment will occur in consultation with the primary care physician.
- Subject accrual, Drop-out rate. Review of the rate of subject accrual and adherence to inclusion/exclusion criteria will occur monthly during the recruitment phase. Drop-out rate will be monitored on a monthly basis.

- Adverse events. In view of the nature of the intervention, we do not expect significant adverse events to occur as a result of the study. Nevertheless, all adverse events will be evaluated by the PI and the mentor within 72 hours (minor or moderate) or 24 hours (serious or fatal), and reported to the IRB of Children's Hospital according to hospital policy. A case report form will be used to monitor adverse events.
- Overall progress of study. The PI will review the safety and progress of this study on a monthly basis. She will also review all data collection forms on a quarterly basis for completeness and accuracy of the data, as well as protocol compliance. The research team will have access to the participant's BodyMedia online activity manager and will observe and intervene with patient.

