6. Risks and Discomforts

The study has been designed to minimize risks and discomforts. Questions about medical and family history, diet and exercise may be distressing for some participants. Referrals to the appropriate professionals will be made available as necessary and on request. However, the participating adolescents have known cardiovascular risk factors that require intervention of some type, and exercise would be indicated for these children. This study has been designed to keep risks to the lowest level possible. A physician will be available on a 24-hr per day basis should any problems arise.

Exercise counseling through the web-based tool will be performed by members of the study team. Any concerns raised as part of this communication will be reviewed every 2 weeks or more frequently as necessary by the study team. Initial consultation with [name], Chief of Psychiatry, or his designate, and with media experts in the Children's Hospital Boston community will be sought prior to the initiation of the protocol to learn from their extensive experience with web-based and internet patient communications.

Data collection will be reviewed regularly for clinically significant abnormalities, and every month by the research team to ensure data collection is proceeding accurately and completely. Results of all clinically relevant tests and procedures will be provided to the parent or guardian of each participant along with an explanation of the results and instructions to contact the child's the primary care physician for appropriate follow-up of abnormal values. Abnormal findings will also be communicated to the participant's primary care physician directly, should the participant authorize this.

Risk of injury will be discussed prior to the exercise program and will be reviewed on a weekly basis to prevent injury from occurring. Muscle soreness is a common discomfort experienced with exercise in the beginner, however not life threatening.

7. Potential Benefits

The potential benefits from participating in this project include possible improvement of cardiovascular risk factors related to increased physical activity. Compensation to families for their time will be provided by way of parking expenses reimbursed, 10.00 gift card or cash incentive when qualifying and arriving for first study visit, and a \$50.00 gift certificate to the subject that has successfully completed the study.

8. Privacy Provisions

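### Between-visit contact, including a weekly injury-risk review, is described only for the intervention arm and no common injury enquiry is scheduled, so recorded injuries may differ by arm through ascertainment.

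*Combined protocol and SAP*

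**What the plan says.** **Injury as a monitored item.** Section 5.f (Data and Safety Monitoring Plan) lists "injury issues related to initiating new physical activities" among its focuses. It is the only physical harm in that list as printed, where the first item is blank. Table 3 sets a quarterly review of adverse events, with injuries in parentheses. The same section provides a case report form for adverse events and requires all of them to be evaluated within 72 or 24 hours, depending on severity. It does not say how or when events are elicited.

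**Contact in the intervention arm.** Section 4.a: "feedback will be provided at least once a week through email and/or phone calls", over 3 months. Section 4.d: "The research team will review patient's data on a weekly basis and discuss the findings via phone or email to promote patient compliance", and staff also answer questions or concerns. Section 4.d also attaches to the FITT prescription "as well as monthly phone follow-up". Section 6: "Risk of injury will be discussed prior to the exercise program and will be reviewed on a weekly basis to prevent injury from occurring".

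**Contact in the control arm.** Controls receive provider counselling in the office. Section 4.d adds: "Participants that do not receive intervention will be provided a personalized FITT exercise counseling session following the study". No study contact with controls is described between baseline and 12 weeks.

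**Scheduled for everyone.** Table 1 has six rows at both visits, from "Height, weight, blood pressure" to a chart review for medical history. None is for injuries or adverse events. Section 4.e gives the questionnaire topics as self-efficacy, social support, perceived barriers and enjoyment.

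**The concern.** An injury can be recorded only if the study team learns of it. Over about 12 weeks, an intervention participant speaks or writes to staff at least weekly and has injury risk reviewed weekly. Those are natural occasions to mention a sprain or soreness. A control participant has no described occasion until the final visit, and no injury question is scheduled there.

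An arm-by-arm listing of injuries would then mix two things: how often injuries happen and how often they are heard about. The programme aims to raise activity, so a true rise in injuries is plausible. An excess in the intervention arm could be a reporting artefact read as harm, or a real excess dismissed as reporting. Whoever reads the quarterly reviews or the pilot's safety summary could not tell which.

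**Working it through.** The plan states no injury rate, capture rate or injury comparison, so there is no figure of its own to reproduce. The check has three steps.

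**1. Routes by which an injury could become known**

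| Route | Intervention | Control |
|---|---|---|
| Weekly phone or email feedback (4.a, 4.d) | yes | not described |
| Monthly phone call with the FITT prescription (4.d) | yes | not described |
| Weekly injury-risk review (6) | yes, by its link to the exercise programme | no study programme until after the study |
| Injury or adverse-event row in Table 1 | none | none |
| Injury among the questionnaire topics (4.e) | none | none |
| Chart review at 12 weeks (Table 1) | yes | yes |
| Unprompted report | possible | possible |

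The scheduled route common to both arms is the chart review. It can find injuries that reached a medical record, but it is not designated for adverse events and is unlikely to find minor injuries or soreness.

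**2. What unequal capture does to counts (all rates assumed)**

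Let n be participants per arm, p the true 12-week injury risk (equal in both arms), and s the probability that an injury is recorded. The expected recorded count is n × p × s. The ratio between arms is s(intervention) / s(control), whatever p is.

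Take n = 30 (enrolled per group, section 5.d), p = 0.20 and s(intervention) = 0.90. The intervention count is 30 × 0.20 × 0.90 = 5.4. P(I > C) is the exact binomial probability that the intervention arm records more injuries.

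| s(control) | Control count | Ratio | P(I > C), p = 0.20 | P(I > C), p = 0.10 |
|---|---|---|---|---|
| 0.90 | 30 × 0.20 × 0.90 = 5.4 | 1.0 | 43% | 41% |
| 0.70 | 30 × 0.20 × 0.70 = 4.2 | 1.29 | 60% | 52% |
| 0.50 | 30 × 0.20 × 0.50 = 3.0 | 1.8 | 76% | 64% |
| 0.30 | 30 × 0.20 × 0.30 = 1.8 | 3.0 | 90% | 76% |

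The ratio column only restates the assumed capture rates. It shows the direction of the effect and is not an estimate of it.

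**3. What a trial of this size could say with equal capture**

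Suppose true risks of 20% and 40% and perfect capture in both arms. Fisher's exact test at two-sided 0.05 then has about 19% power with 20 per arm and about 30% with 30 per arm. A formal injury comparison is out of reach however injuries are collected.

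**The case against.** The strongest case on the other side is that the plan never says injuries are asked about. Section 6 speaks of reviewing risk in order to prevent injury and names no arm. Section 4.d describes the weekly contact in terms of device data, compliance and concerns. A reader might infer about 12 prompted injury enquiries in one arm and none in the other; the documents do not support that count. They show unequal contact, from which unequal opportunity to report follows. That the review covers only the intervention arm is itself an inference, though a strong one, because controls have no study exercise programme during follow-up.

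A reader might also infer that controls contribute only what they volunteer. The chart review at 12 weeks has no restriction by arm and could find medically attended injuries in either. The adverse-event provisions of section 5.f carry no arm restriction either. The case report form and questionnaires themselves are not reproduced, so the absence of any injury question is likely but not proved.

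Finally, section 5.c plans no injury comparison, the aims and hypotheses state no safety question, and Table 3 does not specify a tally by arm. A claim that this gap is what stops the trial answering whether the programme raises injury rates would go too far, since step 3 shows that sample size already does so.

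These points limit the concern but do not remove it. The 72-hour and 24-hour rules act only on events already known, and nothing says how a control's minor injury becomes known.

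**Conclusion.** The point holds as a gap in safety ascertainment. As written, the opportunity to report an injury depends on the arm, and no common enquiry offsets this. Recorded injuries may therefore differ between arms even with equal true risk. It is not shown that they will differ: on the assumed figures above with unequal capture, the intervention arm records more with probability 52% to 90%, against 41% to 43% under equal capture.

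The size cannot be derived from the documents, because it depends on capture rates that they do not give. The conclusion rests on two readings: that the weekly and monthly contacts belong to the intervention arm, and that the unseen forms contain no injury question for all participants. The consequence is for descriptive safety reporting and monitoring; the primary comparison of change in energy expenditure is untouched. The change is worth making because it is nearly free and injury is a harm that the plan itself chose to monitor.

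**What to change.** - Add one or two identical injury questions to the 12-week questionnaire for both arms: any injury since baseline, and whether it led to medical attention or days lost. Add the item to Table 1.
- Ask the same questions at withdrawal of anyone who leaves early. The plan allows for up to 30% attrition, and a 12-week item alone would miss anyone who left because of an injury.
- Designate the existing 12-week chart review as a second common source for medically attended injuries.
- State in section 5.c or 5.f that any by-arm injury statement is descriptive and rests on these common sources. Injuries that surface at weekly contacts should be reported separately, as not comparable across arms.

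The cost is a question or two on a form that all participants already complete, a short withdrawal contact and a reporting sentence. It needs no new visit and no change to the primary analysis. There are two limits. Recall over 12 weeks will miss some minor events, and weekly discussion may sharpen recall in the intervention arm. The bias is therefore reduced rather than removed, and the numbers remain too small for a formal comparison.

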- * see instructions for further information*
